9.3 Interim analyses and Stopping Rules

This is a low risk study consisting of pilot testing an educational intervention. Thus, it is difficult to anticipate specific, a-priori stopping rules. If the research team, IRB, NIA program officer, and/or DSMB identify a pattern to these events, an interim analysis of safety data will be conducted to inform a decision for premature stoppage of study. Since this is a low-risk pilot test of an educational intervention, no interim analyses on the primary study outcomes are planned.

9.4 Data Analyses

SAS software⁷¹ will be used for all analyses. Initial analysis will calculate descriptive statistics at

all data collection points. Outliers will be investigated for accuracy and possible entry errors. Graphic representation of data and correlations among variables will be examined. Patterns and site effects of missing data will be examined in relation to variables of interest.⁷²

Knowledge gain and communication rating data will be compared between the intervention and wait-list control groups and within nursing homes before and after the CHATO training. Changes in knowledge from Time 1 (baseline) to Time 2 will be compared between immediate and wait-listed groups using model estimates obtained with a linear mixed model (LMM) approach to account for repeated measures and clustering within nursing homes. Next, pre- to post-training changes in knowledge will be combined for immediate and wait-list groups and also tested using LMM approach. The models will be adjusted for covariates, such as staff role (RN, LPN, CNA, other), experience, and whether the nursing home has a SCU or not. Distributions of residuals will be evaluated for normality and variance homogeneity and variables will be transformed as needed or statistical analyses for non-normal data will be utilized.

The BPSD and medication reports will be provided for the one-month period before baseline data collection and for each month thereafter until the post-training assessment of the wait-listed nursing homes is completed (a total of seven months for both groups). Resident outcomes data will be compared between the intervention and wait-list control groups and within nursing homes before and after the CHATO training. Seven months of data will be plotted to examine changes in nursing homes and resident outcomes.

We will analyze NH strategies used to engage staff in CHATO (approach, motivation, incentives). Strategies will be described, categorized, and correlated with participation rates. A survey for CHATO group NHs, will describe how CHATO was implemented and concurrent activities that may have influenced BPSD and psychotropic use rates. The Artifacts of Culture Change Tool will describe the NH care environment and practices, leadership and workplace practices, staffing outcomes, and occupancy.¹⁰⁰ In addition, a simple cost-effectiveness analysis (CEA) for the cost associated with hypothesized BPSD reductions will be calculated.

Scores for each engagement strategy category will be calculated, summarized using means and standard deviations, and correlated with participation rates. Strategy categories (approach, motivation, incentives) will be summarized using frequencies and percentages and examined in relation to participation rates using ANOVA or Kruskal-Wallis test, depending on the distribution of participation rates. Participation rates will be calculated using data from the NHs (eligible staff) and from the modules (CHATO participants). Data describing CHATO participant time spent on each module and completion rates, all collected by the learning system, will also be analyzed. We will also evaluate NH attrition and within-NH dropout/completion rates for CHATO participants. We will also evaluate CEA differences for the three typical NH scenarios.⁵⁶

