Our recently completed R01 clinical trial that tested Changing Talk (CHAT) communication training (NR011455) provides preliminary data for the proposed research. CHAT decreased staff elderspeak that reduced resident RTC.³⁰ On average, elderspeak declined from 34.6% (SD = 18.7) at baseline by 13.6 percentage points (SD = 20.00) post-intervention and 12.2 percentage points (SD=22.0) after 3 months (see Figure 1). RTC declined from 35.7% (SD = 23.2) by 15.3 percentage points (SD = 32.4) post-intervention and 13.4 percentage points (SD=33.7) at follow-up. Linear mixed modeling determined that change in elderspeak was predicted by CHAT ($b = -12.20, p = .028$) and baseline elderspeak ($b = -0.65, p < .001$), while RTC change was predicted by elderspeak change ($b = 0.43, p < .001$), baseline RTC ($b = -0.58, p < .001$), resident communication disability, and comorbid illnesses.

[figure not shown]

Figure 1. CHAT effects on elderspeak & RTC.

CHAT increases staff awareness of elderspeak's negative effects and guides practice of more effective communication. CHAT includes three, hour-long sessions, with replicated effects on communication in three studies among staff (N=89) and residents (N=194) in over 20 NHs.³⁰⁻³² Effect sizes ranged from $\eta^2 = .35$ to $.62$ for reducing elderspeak diminutives (inappropriately intimate terms of endearment) and collective “we” pronoun substitutions; effects were maintained

over 2 months. Person-centered (vs task-focused) communication also increased.^{30,33} CHAT was highly rated by past participants (N=217); mean program ratings ranged from 4.5 to 4.8 on a 1 (low) to 5 (high) scale.³⁴

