The PI worked with an instructional designer, item writer, and media team to transition CHAT content, including 20 video clips of NH staff-resident interactions, to the online CHATO modules.³⁷ Scripts from the original CHAT were narrated to maintain content, integrating adult learning theories and principles for online learning, and eliminating a need for advanced literacy skills. Interactive scenario and game-based activities engage staff. For example, participants watch a video clip, select problem communication in the transcript, type their improved communication, and compare it to suggested corrections. Moderated online discussions are included in the modules that are supported on Training-Source.org, a free and publicly available learning portal.

IT functionality and content equivalency of the newly developed CHATO online modules was demonstrated by a convenient university-affiliated sample of nurses, CNAs, and students (N=9) with NH experience. They rated the online modules at 4.7 to 5.0 on a 1 to 5 scale (1 = strongly disagree to 5 = strongly agree) for increasing their knowledge, usefulness, clarity, and satisfaction. CHATO was rated as easy by 57%, while 43% found it somewhat challenging but not too difficult. All reported moderate to great improvement in recognizing and understanding ineffective communication and developing effective communication skills.³⁷ Pre to post test scores improved from $M = 82.4\%$ (SD 10.62) to $M = 91.21\%$ (SD 8.22). Effect sizes for pre-post changes for identifying ineffective, appropriate, and person-centered communication in a video clip were greater for CHATO participants compared to past CHAT participants (N = 217).^{34,37} Although the group testing CHATO may not represent all NH staff, findings confirm that CHATO is feasible and comparable in content and effects.

While CHAT effectively reduced RTC, the in-person classroom format required an onsite interventionist, which limits accessibility and feasibility for dissemination. A pilot test of

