acceptability and preliminary efficacy of online CHATO modules is the next logical step. The pilot will prepare for a pragmatic clinical trial that will test the effects of improved staff communication (from CHATO) on resident BPSD, using available clinical Minimum Data Set (MDS) data. Effects on psychotropic medication use, measured by MDS and Nursing Home Quality Measures (NHQM) data, will also be evaluated. This research will address the gap in rigorous trials testing nonpharmacological interventions to decrease BPSD that also identify strategies to improve intervention dissemination.²⁷ The goal is to increase access to CHATO training, as a tool to reduce BPSD and inappropriate psychotropic medication use to improve dementia care.

3 **STUDY DESIGN**

The R61 will prepare for the R01 pragmatic trial by establishing feasibility of online modules and preliminary efficacy of CHATO with NH staff. The research design is a randomized clinical trial. One NH will provide initial feasibility testing. Any modifications to the modules will be made. Then 6 nursing homes (estimated N=150 staff) will be randomly assigned to intervention or wait-list control groups. The primary outcome will be knowledge gain for staff completing CHATO training. Additional outcomes include resident quality measures related to behavioral and psychological symptoms of dementia (BPSD) on both resident and facility levels and facility level data related to inappropriate use of psychotropic medications to control BPSD.

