Staff Knowledge Gain. At time 1, nursing home staff in both groups will complete baseline pre-tests of knowledge and rating of communication. The immediate intervention group will then complete the online CHATO modules within a one-month period. This includes assessments of post-test knowledge, communication rating, program evaluation, and diffusion of innovation surveys at Time 2. Also, at Time 2, the wait-list control group will repeat the pre-tests of knowledge and communication rating and will then complete the CHATO online module training over a one-month period, followed by Time 3 collection of post-test knowledge, communication rating, program evaluation, and diffusion of innovation surveys. Knowledge gain and communication rating data will be compared between the intervention and wait-list control groups and within nursing homes before and after the CHATO training. Changes in knowledge from Time 1 (baseline) to Time 2 will be compared between immediate and wait-list groups using model estimates obtained with a linear mixed model (LMM) approach to account for repeated measures and clustering within nursing homes. Next, pre- to post-training changes in knowledge will be combined for immediate and wait-list groups and also tested using LMM approach. The models will be adjusted for covariates, such as staff role (RN, LPN, CNA, other), experience, and whether the nursing home has a SCU or not.

TABLE 1. R61 Study Design

Group	Time 1	1 Month	Time 2	1 Month	Time 3
Immediate 3 NHs	Baseline assessment ¹	CHATO training ²	Post-training assessment ³		
Wait list 3 NHs	Baseline assessment ¹		Repeat baseline assessment ¹	CHATO training ²	Post-training assessment ³

¹Pre-test knowledge, Communication rating; ² Three modules over a one-month period;

³ Post-test knowledge, Communication rating, Program Evaluation, Diffusion of Innovation

Resident Quality Measure Outcomes. In addition, nursing homes in both groups will provide monthly summary reports for behavioral symptom occurrence for the facility (in aggregate as well as for individual residents [deidentified]). A nursing home aggregate antipsychotic medication use report will also be collected and analyzed. The BPSD and medication reports will

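### The randomised comparison of knowledge change is not stated to adjust for Time 1 or to assume a common Time 1 mean, so precision may be lost and chance baseline imbalance between three and three homes can enter the estimate

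*Combined protocol and SAP*

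**What the plan says.** Section 3 names the outcome: "The primary outcome will be knowledge gain for staff completing CHATO training". Both arms are tested before training: "At time 1, nursing home staff in both groups will complete baseline pre-tests of knowledge and rating of communication".

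The between-arm analysis appears in Section 3 ("Changes in knowledge from Time 1 (baseline) to Time 2 will be compared between immediate and wait-list groups using model estimates") and again in Section 9.4 ("Changes in knowledge from Time 1 (baseline) to Time 2 will be compared between immediate and wait-listed groups using model estimates"). Section 9.4 obtains those estimates from a "linear mixed model (LMM) approach to account for repeated measures and clustering within nursing homes". The covariate sentence follows: "The models will be adjusted for covariates, such as staff role (RN, LPN, CNA, other), experience, and whether the nursing home has a SCU".

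Neither section writes out the response, the fixed effects or the covariance. The Time 1 score is not among the named covariates, and no common Time 1 mean is stated. A pooled pre-to-post test of both arms follows the between-arm comparison, and neither test is labelled the primary analysis.

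Section 2.2 gives two relevant background results. The earlier CHAT trial's model for change included baseline as a predictor: "and baseline elderspeak ($b = -0.65, p < .001". In an earlier test of the online modules with nine people, "Pre to post test scores improved from $M = 82.4\%$ (SD 10.62) to $M = 91.21\%$ (SD 8.22".

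**The concern.** A repeated-measures model with free arm-by-time means uses the Time 1 score only by subtracting it. That fixes the slope of Time 2 on Time 1 at 1. If the true slope is below 1, the arm that happens to start lower tends to show the larger gain without any training effect, and the interval is wider than it need be.

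There are reasons to doubt a slope of 1 here. The prior pre-test mean was 82.4%, so high scorers have little room to improve. Table 5 lists two test forms, A and B; if staff switch forms between tests, the correlation falls further. In the CHAT trial, change depended on baseline with b = -0.65 for elderspeak and -0.58 for resistiveness to care, which correspond to slopes of 1 - 0.65 = 0.35 and 1 - 0.58 = 0.42. Those are different outcomes, so they only suggest what the knowledge test may do.

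The design cannot secure balance on the pre-test. Six homes are split three and three by simple randomisation, before any data are collected (Sections 6.2.1 and 9.2). What is at stake is the precision of the knowledge outcome's only randomised comparison, and how to read it if the arms start apart.

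**Working it through.** **Inputs from the documents.** Three homes per arm and 150 staff (Sections 3 and 9.2), so m = 25 per home and 75 per arm. Test SD 10.62 and mean gain 91.21 - 82.40 = 8.81 points (Section 2.2, nine people).

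**Assumptions.** ICC 0.02-0.10, pre-post correlation 0.3-0.7 with variants below, equal SDs at both times, 5% two-sided level, t reference with 4 df (multiplier 2.776). The documents give none of these.

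**Plan's own figure.** The 150 is an accrual estimate with no alpha, power, effect size or ICC, so there is nothing to reproduce.

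**Step 1: the contrast.** With complete data and free arm-by-time means, the model's estimate is (mean Time 2 - mean Time 1) in the immediate arm minus the same in the wait-list arm.

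**Step 2: chance imbalance.** The SD of the arm difference in mean pre-test is sqrt(2 x 10.62² x (1 + 24 x ICC) / 75).

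**Step 3: carry-over.** Given a pre-test difference d, the change estimate is expected to move by -(1 - r) x d, where r is the correlation of home means. Shift in points for a 1-SD imbalance:

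| ICC | SD of imbalance | r = 0.3 | r = 0.5 | r = 0.7 |
|---|---|---|---|---|
| 0.02 | 2.11 | 1.48 | 1.05 | 0.63 |
| 0.05 | 2.57 | 1.80 | 1.29 | 0.77 |
| 0.10 | 3.20 | 2.24 | 1.60 | 0.96 |

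If staff and home correlations differ, r = [m x ICC x r_home + (1 - ICC) x r_staff] / [1 + (m - 1) x ICC]. At ICC 0.05 this is (1.25 r_home + 0.95 r_staff) / 2.20. With r_home 0.8, r is 0.67 for r_staff 0.5 and 0.757 for r_staff 0.7. The last gives a shift of 0.243 x 2.57 = 0.63 points.

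**Step 4: precision.** Relative to the imbalance SD, SE(change) is sqrt(2(1 - r)) and SE(baseline-adjusted) is sqrt(1 - r²). The variance ratio is (1 + r)/2: 0.65, 0.75 and 0.85 at r = 0.3, 0.5 and 0.7. At ICC 0.05:

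| r | SE change | SE adjusted | 95% half-width, change | 95% half-width, adjusted |
|---|---|---|---|---|
| 0.50 | 2.57 | 2.23 | 7.1 | 6.2 |
| 0.67 | 2.09 | 1.91 | 5.8 | 5.3 |
| 0.757 | 1.79 | 1.68 | 5.0 | 4.7 |

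**Step 5: six homes, slope estimated.** Step 4 treats r as known. Simulated trials of six homes with 25 staff each gave these variance ratios against the change score:

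- *Time 2 regressed on the individual Time 1 score, random home effect.* 0.64-0.87 with equal correlations at both levels, but 0.97-1.26 at ICC 0.05-0.10 with staff correlation 0.3-0.5 and home correlation 0.9. In such settings the estimate still moved with the imbalance, with a slope of up to +0.44, because the staff-level and home-level slopes differ.
- *Both scores in the response, one common Time 1 mean, home and home-by-time effects.* 0.67-0.99 in every setting run, with residual slopes within about 0.1 of zero.

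Both the change estimator and the individual-score regression averaged close to the true effect in simulation.

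**The case against.** The strongest reply is that the plan leaves the model open rather than choosing a poor one. The covariate list is illustrative, and a repeated-measures model with a common Time 1 mean would already be baseline-adjusted. The earlier CHAT analysis shows that the team uses baseline terms. A reader might infer that the plan rules out baseline adjustment; the text does not support that. What stands is that the plan does not state it, and the usual fit of the model described is a change-score comparison.

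A reader might also infer that the change comparison is biased. It is not, over randomisations. Subtraction already removes most or part of an imbalance, depending on r; only the fraction 1 - r remains, with opposite sign. The 2.2-point shift combines the highest ICC with the lowest correlation; at ICC 0.05 and home-mean correlation 0.50-0.76 the shift is 0.6-1.3 points.

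A third inference would be that this is the declared primary analysis. The documents name knowledge gain as the primary outcome but give neither test that label. This is also a pilot with no stated power or decision threshold for a wider interval to upset.

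Finally, adjustment is not always a gain. With very stable home means and ICC near 0.10, the individual-score regression can be less precise than the change score. That objection stands and determines the form of the fix. It does not apply to the common-mean model, which was no less precise than the change score in any setting run.

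**Conclusion.** The point holds as a modest, inexpensive improvement to the randomised comparison. As usually fitted, the stated model gives a contrast that is unbiased on average, less precise than the data allow, and sensitive to chance pre-test imbalance by about 0.6-2.2 points per SD of imbalance.

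With the common-mean model, the variance should fall by about 20-33% if staff and home correlations are equal at 0.3-0.5, about 7-13% if both are 0.7, and only about 1-20% if the home correlation is 0.9. These figures rest on assumed ICCs and correlations and on SDs from nine people. The CHAT coefficients concern other outcomes and do not establish the slope for this test. Six homes, with about 4 df, limit precision more than the choice of baseline model does.

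**What to change.** In Sections 3 and 9.4, write out the randomised comparison of knowledge as a linear mixed model with:

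- the Time 1 and Time 2 scores both in the response;
- one common Time 1 mean for the two arms, so that the arm effect enters only at Time 2;
- random effects for staff, home and home-by-time;
- a named small-sample df method.

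Use the same form for the communication rating. Keep the unconstrained change comparison as a sensitivity analysis. It also checks the common-mean assumption, which matters because homes are allocated before data collection and staff lists are gathered at each home's initial meeting (Sections 6.2.1 and 6.2.2).

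Do not describe the regression of Time 2 on the individual Time 1 score with a random home effect as equivalent.

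The cost is one model statement in each section. No new data are needed, and staff with only a Time 1 score can remain in the model.

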To evaluate the potential impact of CHAT on psychotropic medication use, we extracted CMS NHQM data for use of antipsychotics for the 10 CHAT NHs for which data were available. We compared each NH's rates for two quarters before and two quarters after each participated in CHAT. The percentage of residents prescribed antipsychotics decreased by an average of 4.9 percentage points, from 20.7% (SD=8.5) to 15.8% (SD=9.0) after CHAT. We used state average rates of antipsychotic medication use for the same time periods to control for changes that may have occurred due to the CMS mandate and other factors.⁴⁷ The state benchmark for prescribed antipsychotics averaged 25.4% across quarters before and declined to 24.9% for quarters after CHAT, a decrease of 0.5%. The average decrease in CHAT NHs (4.9%) compared to the other state NHs (0.5%) was significant ($p=0.05$ for two-tailed t-test).⁴⁸

Despite the success of CHAT in reducing elderspeak and RTC, we found challenges to educating NH staff that limited participation in CHAT including turnover, absenteeism, heavy workloads, and personal conflicts.^{35,36,37} Each CHAT session was held multiple days and times. Still, as few as 44% of staff in one NH completed at least two of the three sessions,³⁰ although this rate is higher than that noted for other NH staff training programs.³⁸ Although successful in reducing RTC, the classroom format limits staff access and participation and feasibility for widespread dissemination. Creative, efficient approaches are needed to overcome NH staff education barriers.^{39,40} We first evaluated online web conference training with multiple NHs as an alternative format for increasing access and dissemination.⁴¹ However, engagement of individual staff was limited with this approach. To facilitate dissemination, online CHAT modules (CHATO) were developed to provide the same CHAT content with asynchronous and independent access for busy NH staff.³⁷

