be provided for the one-month period before baseline data collection and for each month thereafter until the post-training assessment of the wait-listed nursing homes is completed (a total of seven months for both groups). Resident outcomes data will be compared between the intervention and wait-list control groups and within nursing homes before and after the CHATO training. Seven months of data will be plotted to examine changes in nursing homes and resident outcomes.

Implementation Strategies and Process Evaluation. An Implementation Toolkit for NHs and a CHATO Training Manual (See Appendices) have been created to provide support and implementation suggestions to pilot nursing homes. Several consultants provided feedback and additional resources to be included in these materials. Each NH will be given a three-month period to complete the CHATO training. One month for orientation, team development, and planning, one month to complete the three-week training, and one month for staff recognition and follow up. The CHATO Research Team will meet with the NH leadership at the beginning and end of this three-month period, manage CHATO training virtual discussion board, and provide technical assistance as necessary. The process evaluation includes an online implementation survey (See Appendices) which identifies the strategies NHs used to implement the training and includes the Artifacts of Culture survey. The survey uses the Diffusion of Innovation framework and mirrors the Implementation Toolkit. Additional process evaluation activities include: Leadership phone interviews completed by the consultants and external evaluators at LeadingAge and open-ended questions asked of direct care staff in the CHATO virtual discussion.

TABLE 2. R61 Research Timeline

	Quarter 1	Quarter 2	Quarter 3	Quarter 4	Quarter 5	Quarter 6
Planning (IRB, DSMB, Manuals, Measurement)						
Pilot CHATO Modules	—	—	—	—		
Analyses:		—	—	—		
Knowledge Gained			—	—		
Process Evaluation			—	—		
Resident Outcomes			—	—		
Dissemination			—	—	—	—

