6.2.4 Completion and Final Evaluation

Competition

The NH's three-month intervention period will conclude with a closing leadership meeting that will include implementation strategies, challenges and successes, overall lessons learned, collection of surveys, and staff wage data.

- By Closing Leadership Meeting

- Implementation Survey
- The Artifacts of Culture Change Tool
- Staff Wage Data

If NHs need to discontinue study interventions early, circumstances and reasons will be documented. Discontinuation from the CHATO intervention is not anticipated, however, organizational confounds or special circumstances could interfere with participation rate.

Final Evaluation

Deidentified resident data will be provided by Presbyterian Manor for one-month prior to the training and one-month post. External evaluators will conduct leadership phone interviews following the closing leadership meeting. Interviews with leadership staff will provide insight into most effective implementation strategies and overall evaluation of the CHATO training process.

- Final Data Collection

- NH Level, Deidentified Resident Data from executive management
- Leadership Interviews by external evaluator

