9.2 Sample Size and Randomization

Seven NHs will be used to pilot the CHATO intervention during the R61. One nursing home will be used to test overall feasibility. The additional six will be randomized into three intervention and three waitlist controls using a random number generator. We estimate a CHATO training sample size of 150 participants.

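### Resident outcomes are compared before and after training with no control for calendar time, and between arms with no stated months

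*Combined protocol and SAP*

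**What the plan says.** - **Comparison.** Section 9.4 gives the resident analysis in one sentence: "Resident outcomes data will be compared between the intervention and wait-list control groups and within nursing homes before and after the CHATO training". Section 9.1 repeats it. No model, time term, clustering term or comparison window follows.
- **Data.** Reports cover the month before baseline and then continue "for each month thereafter until the post-training assessment of the wait-listed nursing homes is completed" (Section 3, repeated in Sections 9.1 and 9.4), seven months in each arm. The one use stated for the whole series is graphical: "Seven months of data will be plotted to examine changes in nursing homes and resident outcomes".
- **A different data window.** Section 6.2.4 says "Deidentified resident data will be provided by Presbyterian Manor for one-month prior to the training and one-month post".
- **Knowledge outcome.** Section 9.4 is specific here: "Changes in knowledge from Time 1 (baseline) to Time 2 will be compared between immediate and wait-listed groups using model estimates" from a linear mixed model that allows for clustering. Time 2 precedes the wait-list homes' training.
- **Sponsor's earlier study.** For antipsychotic use in the in-person CHAT homes, Section 2.2 reports: "We used state average rates of antipsychotic medication use for the same time periods to control for changes that may have occurred". No such control is carried into Section 9.4.
- **Size.** Section 9.2: "The additional six will be randomized into three intervention and three waitlist controls using a random number generator".

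**The concern.** A before/after comparison within homes attributes to CHATO whatever else changed over those months. Section 2.2 describes a federal mandate and a national partnership that were already pushing antipsychotic use down, and the sponsor allowed for this in the earlier study. The wait-list homes could supply the same control here, but the before/after comparison as stated does not use them.

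The between-arm comparison is randomized, so a shared trend cancels. It needs a window, however. By the end of the series the wait-list homes are trained homes, and in the first post-baseline month or months the immediate homes may not yet be trained. With the window left open, it could be chosen after the plots have been seen.

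Resident outcomes sit under the primary objective in Section 9.1, and Section 2.2 says that the pilot prepares for a trial of effects on BPSD and psychotropic use.

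**Working it through.** **1. Reproducing the seven months.** One pre-baseline month (Sections 3 and 9.4) plus a three-month period per home (Sections 3 and 5.1) for two successive groups gives 1 + 3 + 3 = 7. This matches the stated seven, and the six post-baseline months match the six-month pilot in Section 8. The one-month windows in Section 3's knowledge paragraph and Table 1 give 1 + 1 + 1 = 3, which does not match. I therefore assume month 0 is pre-baseline, months 1–3 are the immediate homes' block and months 4–6 the wait-list homes' block. Section 3's order of planning, training and follow-up puts training in months 2 and 5.

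**2. Trend bias in the before/after comparison.** Let a home count as trained from month s.
- Mean of the months before: (s − 1)/2. Mean of the months from s to 6: (s + 6)/2.
- Gap: (s + 6 − s + 1)/2 = 7/2 = 3.5 months, whatever s is.
- A linear trend of g points a month therefore adds 3.5 × g to a home-effects-only estimate.

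Section 2.2 gives a fall from 20.7% to 15.8% in the CHAT homes (4.9 points) and from 25.4% to 24.9% in the state (0.5 points). The net fall is 4.9 − 0.5 = 4.4 points, and background is 0.5/4.9 = 10% of the crude change. The monthly trends below are assumptions; the second spreads the 0.5 points over six months (0.5/6 = 0.083).

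| Assumed trend, points a month | Bias, points |
|---|---|
| 0.05 | 3.5 × 0.05 = 0.18 |
| 0.083 | 3.5 × 0.083 = 0.29 |
| 0.25 | 3.5 × 0.25 = 0.88 |

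A least-squares check used the 6-home by 7-month layout without noise and a true effect of −4.4. With a trend of −0.083 a month, home effects alone gave −4.69. Adding month effects gave −4.40 for every trend tried. That model has 6 + 6 + 1 = 13 parameters on 42 home-months, and its design has full rank (13 of 13).

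**3. Between arms, if months were pooled.** With a constant effect from onset:

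| Onset of effect | Trained months, immediate / wait-list | Kept over 7 months | Kept over months 1–6 | 7-month loss from wait-list training | 7-month loss from immediate homes' own untrained months |
|---|---|---|---|---|---|
| Start of block | 6 / 3 | 3/7 = 43% | 3/6 = 50% | 3/7 | 1/7 |
| Training month | 5 / 2 | 43% | 50% | 2/7 | 2/7 |
| Month after training | 4 / 1 | 43% | 50% | 1/7 | 3/7 |

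On a 4.4-point effect, pooling would show 4.4 × 3/7 = 1.9 or 4.4 × 0.5 = 2.2 points.

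**4. Which months are clean.** Only the immediate homes are exposed in months 1–3, 2–4 or 3–5 under the three onset rules. Month 3 is clean under all of them, and month 4 under the last two. Stopping before wait-list training is not enough by itself. If the effect starts the month after training, months 1–4 contain two exposed months for the immediate homes and keep 2/4 = 50%; months 1–3 keep 1/3.

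**5. Section 6.2.4.** If its two months are read as those on either side of each home's own training month, immediate homes supply months 1 and 3 and wait-list homes months 4 and 6. The arms then share no calendar month.

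**6. Inference.** There are C(6,3) = 20 allocations of six homes, so the smallest two-sided permutation p is 2/20 = 0.10.

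**The case against.** The plan never says that the arms are compared over all seven months. A reader might infer this, and conclude that the between-arm estimate is biased toward zero. The documents do not support that reading: seven months is the collection and plotting window, and the comparison window is simply not given. The 43% and 50% figures are conditional on pooling, and under two of the three onset rules at least half of the seven-month loss comes from the immediate homes' own untrained months. This part of the objection stands.

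It is also fair to say that the randomized comparison already removes a shared trend; that the antipsychotic trend is small and borrowed from an earlier in-person study; that no BPSD trend is given; and that Section 3 makes knowledge gain primary and resident measures additional. No passage says these estimates will size the later trial. Section 9.4 also plans a survey of concurrent activities that may have affected the outcomes.

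These points limit the size of the problem but do not answer it. The survey describes concurrent activities without adjusting for them. The before/after comparison is a stated analysis with no time control. The contrast with the knowledge outcome, in the same section, shows that the window and model could have been named.

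**Conclusion.** The point holds as a gap in specification and is a cheap improvement. The before/after resident comparison does not separate CHATO's effect from calendar time. On the assumed 1 + 3 + 3 layout with a linear trend, the bias is 3.5 times the monthly trend: about 0.3 points of antipsychotic use if the 0.5-point state decline took six months, and 0.18 to 0.88 points over the assumed range. For BPSD the size cannot be stated.

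The between-arm comparison lacks a window. Loss of half or more of the effect is a risk if months are pooled, not a stated feature of the plan, and wait-list training explains only part of it.

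Two sets of passages conflict whichever analysis is used: Section 6.2.4 against the seven monthly reports, and Section 3's one-month windows against the three-month periods in Sections 3 and 5.1.

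**What to change.** 1. Replace the uncontrolled before/after comparison with one home-by-month (or resident-by-month) mixed model. Include home effects, calendar-month effects and a time-varying indicator for being trained, with one stated rule for when it switches on.
2. Define the between-arm contrast as change from the pre-baseline month to the months after the immediate homes finish training and before the wait-list homes start theirs. On the layout above these are months 3 and 4, or month 3 alone if the onset rule counts from the start of a home's block.
3. Reconcile Section 6.2.4 with the seven monthly reports in Sections 3, 9.1 and 9.4. Reconcile the one-month windows in Section 3 and Table 1 with the three-month periods in Sections 3 and 5.1.
4. Report resident estimates with intervals and call them descriptive. Keep the plots.

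The cost is some wording and one extra model on data already planned. The intervals will be wide with six homes, and the report should say so.
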